## Appendix 2. Clinically Significant Events

Table 5 summarizes the type and severity of symptoms, clinical signs, and clinical laboratory findings that may qualify as a CSE and lead to discontinuation (see section 5.1.2). They are intended as a guideline to the investigator, not as a set of absolute criteria. The underlying principle is to define a level of moderate-to-severe abnormality in safety findings that could cause harm to health, and would preclude further dosing of a subject who experiences this effect. Safety parameters not included in this table may be interpreted in a similar fashion according to investigator judgement.

**Table 5 Clinically Significant Events**

| Parameter                                     | AE level   |
|---|--|
| Symptoms                        |  |
| Severe Hypoglycemia                           | One episode of severe hypoglycemia defined as low blood glucose with mental status impairment severe enough to require third-party assistance.   |
| Severe Nausea and Vomiting             | Requires IV hydration or emergency department visit or hospitalization, or prevents daily activity.  |
| Dizziness/Hypotension                         | Orthostatic CNS symptoms (dizziness, confusion) that are not vasovagal responses to provocative stimuli (for example, phlebotomy, nausea, bowel or bladder function), and are associated with orthostatic SBP decrease >20 mm Hg or DBP decrease >10 mm Hg or heart rate >105 bpm, confirmed to persist for >3 hours |
| Headache/Pain                                 | Any focal or generalized head pain that disrupts normal activities and is not responsive to medical therapies  |
| Pruritus                                      | Generalised itching over >24 hours unresponsive to oral antihistamine  |
| Signs                           |  |
| Systolic blood pressure                       | >30 mm Hg increase from baseline values and an absolute level >190 mm Hg a  |
| Diastolic blood pressure                      | >20 mm Hg increase from baseline values and an absolute level >115 mm Hg a  |
| Heart rate                                    | Resting (sitting or recumbent) HR >120 bpm   |
| QTc   | >500 msec or >60 msec increase from baseline value a  |
| QRS morphology                                | Significant prolongation of QRS interval or new onset of bundle branch block   |
| Clinical Laboratorya |  |
| Hemoglobin                                    | Absolute value <10 g/dL and >2 g/dL reduction from baseline  |
| Neutropenia                                   | Absolute neutrophils <1,500/ $\mu$ L and >1,000 $\mu$ L decrease from baseline   |
| Lymphopenia                                   | Absolute lymphocyte count <800/ $\mu$ L and >500/ $\mu$ L decrease from baseline   |
| Platelet count                                | <75,000/ $\mu$ L and >50,000/ $\mu$ L decrease from baseline   |
| Creatinine                                    | >2 mg/dL and >0.5 mg/dL increase from baseline value   |
| BUN   | >25 mg/L and >10 mg/dL increase from baseline values   |
| Potassium                                     | <2.5 or >5.5 meq/L and >0.5 meq/L change from baseline value   |

*Confidential*

---

| Parameter | AE level  |
|------------------|--|
| Sodium           | <130 or >150 meq/L and >10meq/L change from baseline value |

---

a Must be confirmed by repeat measurement within 48 hours

### Appendix 3. Hepatic Monitoring Tests for Treatment-emergent Abnormality

The following hepatic monitoring tests should be considered for subjects with treatment-emergent hepatic abnormalities to ensure safety and comply with regulatory guidance. If the investigator needs to consider alternative hepatic monitoring tests, and/or strategy, he/she is advised to consult with the sponsor-designated medical monitor prior to testing.

Selected tests may be obtained in the event of a treatment-emergent hepatic abnormality and may be required in follow up with subjects in consultation with the sponsor-designated medical monitor.

#### **Hepatic Hematologya:**

Hemoglobin  
Hematocrit  
Red blood cells (RBC)  
White blood cells (WBC)  
Neutrophils, segmented  
Lymphocytes  
Monocytes  
Eosinophils  
Basophils  
Platelets

#### **Hepatic Chemistrya:**

Total bilirubin  
Direct bilirubin  
Alkaline phosphatase (ALP)  
Alanine aminotransferase (ALT)  
Aspartate aminotransferase (AST)  
Gamma-glutamyl transferase (GGT)

#### **Haptoglobina**

#### **Hepatic Coagulationa**

Prothrombin Time  
Prothrombin Time, INR (international normalized ratio)

#### **Hepatic Serologiesb**

Hepatitis A antibody, total  
Hepatitis A antibody, IgM  
Hepatitis B surface antigen  
Hepatitis B Core antibody  
Hepatitis C antibody  
Hepatitis E antibody, IgG  
Hepatitis E antibody, IgM

#### **Anti-nuclear Antibodya**

#### **Anti-smooth muscle Antibodya**

a can be assayed by either sponsor-designated laboratory or local laboratory

b reflex/confirmation dependent on regulatory requirements and/or testing availability

1 SUMMARY OF CHANGES

SAP Version History		
Version	Date	Description of Changes
1.0	Jan. 15, 2019	Original signed version.
2.0	Feb. 4, 2019	CCI [REDACTED] [REDACTED] [REDACTED] [REDACTED]

2 INTRODUCTION

This Statistical Analysis Plan (SAP) provides a description of the statistical methods and procedures to be implemented for the analyses of efficacy and safety data from OPKO Ireland Global Holdings Ltd. Protocol DPO-203. Any deviations from this analysis plan will be substantiated by sound statistical rationale and will be documented in the final clinical study report. Analysis of immunogenicity CCI [REDACTED] analysis will be addressed in separate reports.

3 STUDY OBJECTIVES

3.1 Primary Objective

To evaluate the effect of dose escalation of once-weekly (QW) subcutaneous (SC) OPK-88003 versus placebo injections on HbA1c absolute change from baseline to after 30 weeks treatment in subjects with type 2 diabetes mellitus (T2DM) inadequately controlled with diet and exercise alone, or treated with a stable dose of metformin.

3.2 Secondary Objectives

The secondary objectives of this study are to determine the effect of OPK-88003 vs placebo on:

1. Mean percent (%) body weight change from baseline to after 30 weeks treatment,
2. Percent (%) of subjects with 5% or greater body weight loss after 30 weeks treatment,
3. Change of fasting plasma glucose (FPG) from baseline to after 30 weeks treatment, and
4. Number and percent (%) of subjects achieving HbA1c \leq 6.5%.

3.3 Other Objectives

Other objectives of this study are as follows:

CCI

3. Percent (%) of subjects permanently discontinued from the study due to hyperglycemia;
4. Incidence and rate of gastrointestinal (GI) events, major cardiovascular (CV) events, hypoglycemia, injection site reactions, hypersensitivity reactions and pancreatic events;
5. To evaluate immunogenicity of OPK-88003 (a separate ADA report will be provided);

CCI

[figure not shown]
4 STUDY OVERVIEW

4.1 Study Design

Study DPO-203 is a randomized, double-blind, dose escalation, placebo-controlled, phase 2 multicenter trial in subjects with T2DM. There will be up to approximately 30 investigational sites. The trial consists of four phases: a screening/baseline phase (up to 2 weeks prior to first dose), a 30-week treatment period consisting of a dose escalation phase (8 weeks) and a target dose phase (22 weeks), and a follow-up period (4 weeks). Subjects will be randomly assigned to OPK-88003 or placebo administered QW. CCI

CCI

Study Design for DPO-203

EOT: end of treatment
↓ indicates dosing

The schedule of events for the study is provided in Protocol Appendix 1.

4.2 Randomization and Treatments

Subjects who meet all eligibility criteria will be randomized to treatment at visit 2 (day 1) via the Interactive Response Technology system (IRT). Randomization will be stratified using the following variables: screening HbA1c ($<8.5\%$, $\geq 8.5\%$) and baseline body mass index (BMI) (<30 , ≥ 30 kg/m²). The randomization to the treatment arms will be 1.75:1 for the active and placebo groups, respectively. Following randomization, study drug will be dispensed in a double-blinded manner. OPK-88003 and matching placebo are provided in single-use 2 mL glass vials with blue flipoff lid, an aluminum seal and a rubber stopper (septum).

This trial will evaluate 20 mg and 40 mg dose escalation and 70 mg target dose of OPK-88003 QW over a 30-week treatment period. Treatment allocation will be assigned by the IRT. The group randomized to OPK-88003 will initially receive 20 mg QW for four weeks, followed by 40 mg QW for four weeks. Once eight weeks of dose escalation are complete, subjects will receive a target dose of 70 mg QW OPK-88003 for 22 weeks. The control group will receive matched placebo SC injections QW for 30 weeks.

5 ANALYSIS ENDPOINTS

5.1 Primary Efficacy Endpoint

The primary efficacy endpoint is absolute change in HbA1c from baseline to Week 30. If the Week 30 measurement is missing, the last valid post-baseline observation (last post-baseline observation carried forward [LOCF]) algorithm will be applied to impute the missing Week 30 value only for subjects that have discontinued early due to hyperglycemia (Week 30/LOCF_H). Otherwise, no imputation will be made for the missing Week 30 values.

5.2 Secondary Efficacy Endpoints

- Percent (%) change in body weight from baseline to Week 30,
- Number and percent of subjects with 5% or greater body weight loss at Week 30 (i.e. percent change $\leq -5\%$),
- Absolute change in FPG from baseline to Week 30/LOCF_H, and
- Number and percent of subjects achieving HbA1c $\leq 6.5\%$ at Week 30/LOCF_H.

5.3 Additional Secondary Endpoints

- Absolute change in body weight from baseline to Week 30;
- Absolute change and percent (%) change in body weight from baseline to Weeks 4, 8, 12, 16, 22, 26, 30, and 34 without LOCF;
- Number and percent of subjects achieving $\geq 5\%$ weight loss at Weeks 4, 8, 12, 16, 22, 26, 30, and 34 without LOCF;
- Absolute change in FPG from baseline to Weeks 4, 8, 12, 16, 22, 26, 30/LOCF_H, and 34;
- Absolute change in HbA1c from baseline to Weeks 4, 8, 12, 22, 30/LOCF_H, and 34;
- Number and percent of subjects achieving HbA1c $\leq 6.5\%$ at Weeks 4, 8, 12, 22, 30/LOCF_H, and 34;
- Number and percent of subjects achieving HbA1c $< 7.0\%$ at Week 30/LOCF_H; and
- Number and percent of subjects achieving HbA1c $< 7.0\%$ at Weeks 4, 8, 12, 22, 30, and 34 without LOCF.

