## 5.2 Discontinuation of Subjects

If the investigator site identifies a subject who did not meet eligibility criteria but was inadvertently randomized, the sponsor-designated medical monitor must be contacted.

If the sponsor or designee identifies a subject who did not meet enrollment criteria and who was inadvertently randomized, the investigator site will be notified. A discussion must occur between the sponsor-designated medical monitor and the investigator to determine whether the subject may continue in the study. Inadvertently randomized subjects may be maintained in the study when the sponsor agrees with the investigator that it is medically appropriate for that subject. The investigator must obtain documented approval from the sponsor to allow the inadvertently enrolled subject to continue in the study.

A subject will be discontinued from the study in the following circumstances:

- The subject requests to be withdrawn from the study.
- The subject is permanently discontinued from study drug (see section [5.1.2](#)).
- The subject misses more than four doses of study drug over the course of the study, or misses two consecutive doses of study drug during the dose escalation phase.
- Enrollment in any other interventional clinical trial.
- The sponsor stops the study or stops the subject's participation in the trial for medical, safety, regulatory or other reasons consistent with applicable laws, regulations and good clinical practice (GCP).

- The investigator decides it is in the best interests of the subject not to continue in the study.
- The subject and/or blinded study staff become unblinded to the subject's treatment assignment.
- Any medication for weight loss is given for more than one week.
- If the subject, for any reason requires treatment for greater than one week with another therapeutic agent that has been approved for treatment of diabetes. A change in dose of metformin is not allowed, unless a temporary increase in dose is needed to treat hyperglycemia (see section 6.11). However, a change to an equivalent dose strength of metformin from immediate-release to extended-release (or vice versa) formulations is allowed.

Subjects discontinued from the study will be requested to complete an early termination (ET) visit as soon as possible (section 9.5). Subjects will be requested to complete a follow-up visit (see section 9.5) four weeks after their final dose.

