6.2 Baseline, Endpoint, and Other Statistical Considerations

The clinical statistical efficacy and safety analyses will be performed by Medpace.

First dose of study drug refers to the first dose of blinded study drug (Week 0 Day 1).

Baseline will be the measurement at Week 0 Day 1. If missing, the last valid measurement prior to the first administration of study drug will be used as baseline.

Any measurements/events that occur after the subject started rescue therapy will not be included in the efficacy analyses.

Unless specified otherwise, treatment groups will be OPK-88003 and placebo for summaries and analyses. Additional explorations may be done by OPK-88003 dose.

Descriptive statistics (n, mean, standard deviation, median, minimum, and maximum) will be used to summarize the continuous efficacy and safety data by treatment group. The count and frequency will be used to tabulate categorical measurements.

Data will be used as it is reported. LOCF may be used when specified. The value must be collected within the last dose date +10, inclusive, in order to be used as LOCF. Where specified, LOCF_H (for subjects that have discontinued early due to hyperglycemia) or LOCF_{All} (for all subjects) may be used.

No adjustments for multiplicity will be performed. All tests of treatment effects will be conducted at a two-sided alpha level of 0.05 and/or two-sided 95% confidence interval (CI), unless otherwise stated.

Analysis Visit Windows

For all efficacy and safety assessments, analysis visits will be assigned according to the actual study day, calculated as the assessment date – first dose date for assessments prior to the first dose date and assessment date – first dose date +1 for assessments on or after the first dose date. The analysis visit windows will be defined as the halfway point between the target visit days:

Analysis Visit	Target Visit Day	Analysis Visit Window (Days)
Visit 1 (Screening)	N/A	N/A
Baseline	1	≤ 1
Visit 3 (Week 1)	8	2 – 18
Visit 4 (Week 4)	29	19 – 43
Visit 5 (Week 8)	57	44 – 60

Analysis Visit	Target Visit Day	Analysis Visit Window (Days)
Visit 6 (Week 9)	64	61 – 67
Visit 7 (Week 10)	71	68 – 74
Visit 8 (Week 11)	78	75 – 81
Visit 9 (Week 12)	85	82 – 99
Visit 10 (Week 16)	113	100 – 134
Visit 11 (Week 22)	155	135 – 169
Visit 12 (Week 26)	183	170 – 197
Visit 13 (Week 30)	211	198 to \leq last dose date + 10
Visit 14 (Week 34/Follow-up)	239	N/A

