6.9 Efficacy Analysis

6.9.1 Primary Efficacy Endpoint

The primary efficacy analysis is to evaluate the effect of dose escalation of OPK-88003 versus placebo injections on HbA1c absolute change from baseline to Week 30. If the Week 30 measurement is missing, the LOCF algorithm will be applied to impute the missing Week 30 value only for subjects that have early terminated due to hyperglycemia (Week 30/LOCF_H). Otherwise, no imputation will be made. The primary analysis will be based on the mITT Population. The same analysis will be repeated on the PP Population.

The change from baseline in HbA1c at each scheduled visit will be analyzed using a mixed-model repeated-measures (MMRM). The factors in the model will be BMI strata, treatment group, baseline HbA1c value, visit, and the treatment group by visit interactions. An unstructured covariance matrix will be used (TYPE=UN). No imputation will be performed except for subjects that early term due to hyperglycemia. The least-squares means for change from baseline at each visit will be estimated and compared between treatment groups, with Week 30 being primary, and no adjustments for multiplicity. The sample SAS code can be found below:

```
*****
Note:
  USUBJID = unique subject identifier
  TREATMENT = 0 (placebo), 1 (OPK-88003)
  BMI: <30 or >=30 kg/m2
  VISIT = visit
  BASE = baseline value
  CHG = change from baseline to the specified visit
*****;
proc mixed;
  class USUBJID BMI TREATMENT VISIT;
  model CHG = BMI TREATMENT BASE VISIT TREATMENT*VISIT;
  Repeated VISIT / TYPE=UN sub=USUBJID;
  lsmeans VISIT*TREATMENT / cl slice=VISIT;
run;
```

CCI

CCI [REDACTED]

Supportive Analysis

If the Week 30 HbA1c measurement is missing, the LOCF algorithm will be applied to impute the missing Week 30 value for all subjects (Week 30/LOCF_{All}). The change from baseline to Week 30/LOCF_{All} in HbA1c will be analyzed using linear contrasts from an analysis of covariance (ANCOVA) model with treatment group and BMI strata (<30, ≥30 kg/m²) as factors and the baseline HbA1c value as a covariate. The least-squares means, standard errors, and the 2-tailed 95% confidence intervals (CIs) for each treatment group and for comparison of OPK-88003 to placebo will be presented. The 2-sided p-values testing for significance within treatment group change from baseline and comparison between treatment groups will be presented.

The sample SAS code can be found below:

```
*****
Note:
  TREATMENT = 0 (placebo), 1 (OPK-88003)

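### Early leavers' off-drug follow-up values can enter the repeated-measures model that gives the Week 30 HbA1c contrast, because the SAP neither lists the model's visits nor settles how Visit 14 is assigned

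*SAP*

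**What the plan says.** - **Time points.** SAP 5.3 includes Week 34 for HbA1c ("Absolute change in HbA1c from baseline to Weeks 4, 8, 12, 22, 30/LOCF_H, and 34"), and likewise for body weight and FPG.
- **Primary model.** SAP 6.9.1: "The change from baseline in HbA1c at each scheduled visit will be analyzed using a mixed-model repeated-measures (MMRM"; "An unstructured covariance matrix will be used (TYPE=UN"; "No imputation will be performed except for subjects that early term due to hyperglycemia". The Week 30 contrast is primary. SAP 6.9.2.2 and 6.9.2.3 use the same kind of model for weight and FPG. None of these sections lists the levels of VISIT or excludes Visit 14.
- **Follow-up.** Protocol 9.5 collects HbA1c, fasting glucose and weight at Visit 14. Completers attend around day 239. For early leavers, Protocol 5.2 says: "Subjects will be requested to complete a follow-up visit (see section 9.5) four weeks after their final dose".
- **Visit assignment.** SAP 6.2 labels the last visit "Visit 14 (Week 34/Follow-up", with target day 239 and N/A as its window. The same section says of all efficacy and safety assessments: "analysis visits will be assigned according to the actual study day".
- **Off-drug limits.** The Week 30 window closes 10 days after the last dose, and for carrying values forward, "The value must be collected within the last dose date +10, inclusive, in order to be used as LOCF". No other analysis window has such a limit. The only general efficacy exclusion is data after rescue therapy.

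**The concern.** The objective is the HbA1c change after 30 weeks of treatment, and the SAP takes care to keep late off-drug values out of Week 30 and out of LOCF. In an unstructured repeated-measures model, however, a subject's value at any visit helps predict that subject's missing Week 30 value. If an off-drug follow-up value sits in the model under any visit name, the excluded information returns through the covariance.

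The subjects who matter are early leavers, and SAP 8.2 reports more of them than expected, particularly early in the study. At stake is a Week 30 contrast that mixes on-drug and off-drug response, in proportions set by how many leavers come back. Under label assignment, the Week 34 summaries would also combine follow-up after a few doses with follow-up after the full course.

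**Working it through.** **1. Where a leaver's follow-up lands.** A last dose at week w falls on day 7w + 1. Follow-up four weeks later falls on day 7w + 29.

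| Last dose | Follow-up day | Days before day 239 | By label | By study day (SAP 6.2 window) |
|---|---|---|---|---|
| Week 0 | 29 | 210 | Week 34 | Week 4 (19–43) |
| Week 4 | 57 | 182 | Week 34 | Week 8 (44–60) |
| Week 8 | 85 | 154 | Week 34 | Week 12 (82–99) |
| Week 12 | 113 | 126 | Week 34 | Week 16 (100–134) |
| Week 22 | 183 | 56 | Week 34 | Week 26 (170–197) |

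Every one of these values is 28 days after the last dose, so all fail the 10-day limit, but that limit applies only to Week 30 and LOCF. HbA1c is not scheduled at Weeks 16 and 26. For HbA1c the study-day reading therefore matters mainly when follow-up falls in the Week 4, 8, 12 or 22 windows. Weight and FPG are scheduled at all of them.

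For a completer with a last dose at Week 29 (day 204), the Week 30 window closes on day 204 + 10 = 214. Visit 14 at day 239 ± 4 is 31 to 39 days off drug.

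**2. Who can move Week 30.** Four groups need separating:
- Completers with a Week 30 value: Week 34 adds nothing about a value already observed.
- Leavers for hyperglycemia: those with an LOCF_H value have Week 30 filled.
- Measurements after rescue: already excluded.
- Other leavers with no Week 30 value who attend follow-up: the model predicts their Week 30 partly from the off-drug value.

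Only the last group causes the pull. Under label assignment, the link from Week 34 to Week 30 is estimated from completers, whose Week 34 follows a full course of treatment.

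**3. The plan's own power figure, as a scale.** With SD 1.0 and 48 v 27 subjects, SE = √(1/48 + 1/27) = 0.241. Power = Φ(0.8/0.241 − 1.96) = Φ(1.37) = 0.914 (0.907 by noncentral t). This agrees with the stated minimum of 90%.

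**4. Size of the pull on HbA1c.** Two simulations fitted arm-by-visit means and a common unstructured covariance by maximum likelihood, with a true Week 30 contrast of -0.80. The inputs on dropout, attendance, correlation and loss of effect are assumptions; the documents do not give them.

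- *70 v 40 subjects.* Dropout 20–30% at Weeks 4–20, 50–90% of leavers attending follow-up, 30–70% of the effect lost by then. Adding follow-up as Week 34 moved the contrast toward zero by about 0.01 to 0.09. Example (30% dropout, 90% attending, 70% lost): -0.81 without, -0.72 with.
- *30,000 subjects per scenario.* Dropout 20–40% active and 20–30% placebo, mostly early and at random; correlation 0.7–0.9 per 8 weeks; 50–90% of the effect kept at completers' Week 34; 0–70% of the effect so far kept at leavers' follow-up; every leaver attending; baseline terms omitted. One scenario (dropout 30% v 20%, correlation 0.9, 70% and 50% kept):

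| Data in the model | Week 30 contrast |
|---|---|
| No Week 34 | -0.807 |
| Week 34 from completers only | -0.807 |
| Leavers' follow-up labelled Week 34 | -0.719 |
| Leavers' follow-up placed by study day (Weeks 8/12) | -0.752 |

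Across the second set, the pull was 0.06 to 0.15 under label assignment and 0.02 to 0.11 under study-day assignment.

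**5. On the power scale.** A contrast of 0.80 − 0.06 = 0.74 gives Φ(0.74/0.241 − 1.96) = 0.87. A contrast of 0.80 − 0.15 = 0.65 gives 0.77. These hold the SE fixed at 48 v 27 and show scale only.

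**The case against.** The strongest reply is that the SAP already assigns every assessment by actual study day, and that the visit label only breaks ties within a window. On that rule a day-85 follow-up is a Week 12 value, and Week 34 is not mislabelled. This stands against the stronger inference that leavers' follow-ups must take the Week 34 label: the N/A window suggests it, but the study-day rule contradicts it. It does not protect Week 30, because the off-drug values then sit in on-treatment windows that have no last-dose limit.

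Second, Week 34 as a level of the primary model is inferred. It is the natural reading of SAP 5.3 with 6.9.1, but the SAP does not state it. Text after the sample code in 6.9.1 is redacted and might list the visits.

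Third, safeguards exist. The per-protocol repeat drops subjects who withdrew before Week 26 for reasons other than hyperglycemia, and the supportive LOCF_All ANCOVA cannot use values beyond last dose plus 10 days. Both are largely free of the problem. They are cross-checks, though, and a difference between them and the primary result would have several possible explanations.

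Fourth, the pull is below one standard error: 0.01/0.241 = 4% to 0.15/0.241 = 62%. The upper end needs high dropout and full follow-up attendance together. That is fair, and it is why the size is given as a range.

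**Conclusion.** The point holds in a limited form. As written, on either reading of SAP 6.2, off-drug values from leavers without a Week 30 value can inform the primary Week 30 estimate, against the SAP's own 10-day principle. For HbA1c the pull is roughly 0.01 to 0.15 points toward zero from -0.8, or about 1% to 19% (0.01/0.8 to 0.15/0.8). Both size and direction rest on assumed dropout, attendance, correlation and loss of effect. Under label assignment, the direction depends on leavers showing less effect at follow-up than completers do at Week 34.

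A reader might infer that Week 34 data as a whole contaminate Week 30. They do not: follow-up from completers with a Week 30 value leaves it unchanged. A reader might also want a figure for body weight. The mechanism is the same, but the documents give no placebo-adjusted percentage contrast or SD from which to size it, so none is offered. This should be corrected, because it touches the primary contrast and the repair is small.

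**What to change.** - **SAP 6.9.1, 6.9.2.2, 6.9.2.3:** list the MMRM visits and remove Visit 14 from VISIT. HbA1c: Weeks 4, 8, 12, 22 and 30. Weight and FPG: Weeks 4, 8, 12, 16, 22, 26 and 30.
- **SAP 6.2, on-treatment windows:** apply the existing limit of last dose plus 10 days to every efficacy window from Week 4 to Week 30. Removing Visit 14 alone would not close the study-day route.
- **SAP 6.2, Visit 14:** give it a day window around day 239, and count as Week 34 only subjects who completed the 30-week treatment period.
- **SAP 5.3 and 6.9.2:** report Week 34 descriptively as an off-drug result, and end the by-visit responder comparisons at Week 30. Summarise leavers' follow-up separately, by days since last dose.
- If off-drug data are wanted in the estimate, name a treatment-policy estimand and model by actual study time.

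The cost is SAP wording and a data subset, settled before unblinding. All follow-up values are still reported. Two things are lost: a model-based Week 34 comparison that includes early leavers, and the use in the model of any early-termination value taken more than 10 days after the last dose.
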